B-type natriuretic peptides are a cardiac neurohormone secreted from the atria and ventricles in response to volume expansion. This natriuretic peptide system assists in regulating extracellular volume by inducing renal diuresis.⁵⁹ Serum levels of BNP increase in cardiac disease conditions associated with increased atrial and ventricular stretch and left ventricular diastolic filling pressures. Miller et al. found that BNP concentrations were increased in outpatients with HF and were directly correlated with the magnitude of HF.⁶⁰ In one study of 1,653 subjects, the BNP levels increased as left ventricular dysfunction increased.⁶¹ Ruskoaho found that in the outpatient setting serum BNP values had a sensitivity of 97% and a negative predictive value of 98%.⁶² Increased BNP concentrations with diastolic dysfunction have been strongly related to left ventricular hypertrophy.⁶³ HF recommendations were updated in 2010 to include natriuretic peptides (i.e., BNP) in the urgent-care setting when the clinical diagnosis of HF is uncertain.⁶⁴ In HF patients with EF > 40%, natriuretic

peptides were the strongest independent predictor of diastolic dysfunction.⁶⁵ At time of discharge, a BNP level of 400 pg/ml was 89% sensitive for events, and the negative predictive value was 96%.⁶⁶ Independent of other prognostic variables, BNP levels have been shown to predict mortality in patients with HF.⁶⁷

BNP concentration will be measured using a portable i-STAT handheld analyzer. A blood sample (20 µl) will be obtained from a finger stick after the subjects have completed the questionnaires at baseline and 12 weeks. We will measure BNP concentration at each visit. Prior to running the BNP test, the cartridge initiates a series of preset quality control diagnostics, from monitoring the quality of the sample to validating the reagent. The i-STAT can detect BNP levels ranging between 5 and 5000 pg/ml, with results available in 10 minutes.

Hypothesis #6. Ubiquinol (600 mg daily), D-ribose (15 g daily), or a combination of the two will decrease the lactate/ATP ratio in patients with HFpEF.

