|-----------------------------|------------------------|------------------------------------|------------------------------|------------------------------------|
| | Baseline | Change after 12 weeks ^a | Baseline | Change after 12 weeks ^a |
| KCCQ Clinical Summary Score | 48.0 ± 21.9 | +16.3 ± 7.0 | 42.2 ± 28.3 | +30.0 ± 13.2 |
| Functional Status | 46.6 ± 22.6 | +16.3 ± 8.5 | 39.4 ± 29.3 | +31.7 ± 12.3 |
| Self-efficacy | 57.5 ± 16.8 | +15.0 ± 10.5 | 62.5 ± 16.3 | +12.5 ± 8.8 |
| Social Interactions | 56.0 ± 20.1 | +12.0 ± 7.6 | 53.0 ± 22.0 | +22.0 ± 17.5 |
| Quality of Life | 43.3 ± 29.7 | +23.3 ± 12.4 | 40.0 ± 34.1 | +33.3 ± 13.2 |
| Symptoms | 46.0 ± 25.1 | +16.0 ± 10.7 | 39.0 ± 29.3 | +38.5 ± 12.9 |
| Physical Limitation | 47.3 ± 19.6 | +16.7 ± 6.2 | 40.0 ± 29.7 | +22.7 ± 13.6 |
| Vigor Score (POMS) | 15.2 ± 10.7 | +7.6 ± 4.2 | 8.8 ± 9.3 | +9.6 ± 3.0 |

Values are mean ± standard deviation. a: For each patient, a change in a variable was computed by subtracting the baseline variable measure from a measure taken at the end of 12 weeks.

Table 2 presents a summary of echocardiographic data from a retrospective chart review of patients with HFpEF: E/e' ratio; pulmonary artery pressure; and B-type natriuretic peptide (BNP) levels. Variables were retrieved from charts before and 12 weeks after taking the supplements (ubiquinol 600 mg/day, D-ribose 15 grams/day).

[figure not shown]
| Table 2 Variable | No Ubiquinol | | With Ubiquinol | | With Ubiquinol + D-ribose | | Observed Effect Size Ubiquinol | Observed Effect Size Ubiquinol+ D-ribose ^e |
|---------------------------|--------------------|------------------------------------|-------------------|------------------------------------|---------------------------|------------------------------------|--------------------------------|---|
| | Baseline | Change after 12 weeks ^a | Baseline | Change after 12 weeks ^b | Baseline | Change after 12 weeks ^c | | |
| E/e' ratio | 9.3 ± 2.4 (N=6) | +5.5 ± 2.4 | 17.9 ± 6.1 (N=8) | -7.7 ± 4.6 | 18.2 ± 4.2 (N=8) | -6.5 ± 2.9 | -3.5 | -4.4 |
| Pulmonary Artery Pressure | 32.1 ± 5.4 (N=12) | +13.2 ± 8.6 | 37.8 ± 5.8 (N=10) | -13.6 ± 10.3 | 41.1 ± 5.9 (N=8) | -10.4 ± 6.0 | -2.8 | -3.3 |
| BNP (pg/ml) | 1892 ± 2381 (N=13) | +4598 ± 4986 | 2194 ± 1806 (N=8) | -1494 ± 1641 | 2122 ± 116.5 (N=4) | -1262.8 ± 92.7 | -1.5 | -1.3 |

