Analogous two-tailed independent samples t-tests will be used to compare changes in POMS scores. According to a linear regression of changes in POMS Vigor scores versus changes in the KCCQ Clinical Summary scores using our pilot data, a 10-point increase in KCCQ Clinical Summary scores predicted about a 6.5 point increase in Vigor scores. Thus, we believe that a 6.5-point increase in vigor in our subjects will be of clinical importance. Our pilot study also yielded an estimated standard deviation of 3.6 for 12 week changes in Vigor score, which implies that Cohen effect sizes of at least 1.8 are clinically important. Our sample sizes will provide 99% power to detect this or larger effect sizes at a nominal 0.05 significance level with Bonferroni correction for four comparisons. If assumptions of the t-test are not satisfied, transformations or the Mann-Whitney test will be applied. The five subjects of our pilot study who received ubiquinol showed a significant increase of 16.3 points in KCCQ Clinical Summary scores with respect to baseline ($t=5.23$, $df=4$, two-tailed paired samples $p=0.0064$). Similarly, the other five subjects of our pilot study who received ubiquinol + D-ribose showed a significant increase of 30 points with respect to baseline ($t=5.10$, $df=4$, two-tailed paired samples $p=0.007$). The 13.7-point increase produced by the independent effect of D-ribose was borderline significant ($t=2.06$, $df=9$, two-tailed independent samples $p=0.08$). These results from our small pilot study suggest a high likelihood that ubiquinol, and probably D-ribose, will produce clinically important increases of 10 points in KCCQ scores, which gives additional confidence in the success of our proposed study and in the potential clinical applications of ubiquinol.

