Hypothesis #4. A two-tailed independent samples t-test will be used to test the null hypothesis that the mean change in the 6MWT from baseline to the end of 12 weeks in patients taking ubiquinol is different from the mean change for placebo. Comparisons of D-ribose versus placebo, of ubiquinol + D-ribose versus placebo, and of ubiquinol versus ubiquinol + D-ribose will likewise be made. Our proposed sample sizes (62 per group) will allow detecting Cohen effect sizes on the 6MWT of at least 0.7 with at least 90% power at a nominal 0.05 level of significance with Bonferroni correction for four comparisons. Published data⁸⁶ suggest the possibility of a much larger effect size of ubiquinol on a 6-minute walk (3.9), giving us confidence in our design for at least the ubiquinol vs. placebo comparison.

Hypothesis #5. Our pilot data suggested that ubiquinol has a large effect size on BNP (-1.5 ; Table 2). Thus, two-tailed independent samples t-tests comparing changes in BNP from baseline to the end of 12 weeks will have a large power (99%) for investigating Hypothesis #5 using Bonferroni corrections. In general, our sample sizes will be able to detect effect sizes of at least 0.7 in absolute value with at least 90% power.

Hypothesis #6. The change in lactate/ATP ratio from baseline to 12 weeks will be computed for each patient. A one-tailed independent samples t-test will examine the null hypothesis of no differences in mean changes

between ubiquinol and placebo groups against the alternative that the mean change in patients on ubiquinol will be numerically smaller, which includes the possibility of a negative change. Similar tests will compare D-ribose versus placebo, the combination of ubiquinol + D-ribose versus placebo, and ubiquinol versus ubiquinol + D-ribose. Our sample sizes will give us a power of at least 90% to detect effect sizes of at least 0.7 in absolute value by using a 0.05 significance level and Bonferroni correction for the four comparisons.

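### Hypothesis 5 tests raw BNP change without baseline adjustment, although the pilot values imply strong skew; no log scale is fixed in advance, and there is no rule for readings outside the assay range

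*Combined protocol and SAP*

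**What the plan says.** Section C.5, Hypothesis #5, specifies "two-tailed independent samples t-tests comparing changes in BNP from baseline to the end of 12 weeks", with Bonferroni corrections. It names no transformation and no adjustment for baseline BNP. It claims 99% power on the strength of a pilot effect size of -1.5, and adds that "our sample sizes will be able to detect effect sizes of at least 0.7 in absolute value with at least 90% power".

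The pilot effect size comes from Section C.4, Table 2, a nonrandomised chart review. The BNP entry for patients without ubiquinol reads "1892 ± 2381 (N=13) | +4598 ± 4986" (baseline, then change after 12 weeks).

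Section C.3, Hypothesis #5, describes the handheld assay: "The i-STAT can detect BNP levels ranging between 5 and 5000 pg/ml". No section says how a reading outside those limits is to be recorded or analysed.

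The only fallback for the t-tests is "If assumptions of the t-test are not satisfied, transformations or the Mann-Whitney test will be applied". It appears within the Hypotheses #1 and #2 text, after the POMS comparison. A separate sentence under the interaction analyses allows transformations, but for regression models.

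**The concern.** BNP cannot be negative, so a baseline SD larger than the mean points to a long right tail. The SDs of change also differ widely between the pilot groups (4986, 1641 and 92.7). If treatment lowers BNP by a proportion, the change in pg/ml grows with the starting value. A few patients with very high BNP then dominate both the mean difference and its standard error.

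It would be left to the analyst, after seeing the data, to decide whether the fallback reaches Hypothesis 5, what would trigger it and which transformation to use. That choice can decide whether a moderate effect is declared. The missing rule for readings above 5000 pg/ml leaves another decision open until the data are in.

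**Working it through.** **Inputs.** Evaluable patients per group: 62 (C.5). Alpha: 0.05/4 = 0.0125 two-sided. Hypothesis #5 mentions only Bonferroni corrections; the count of four is taken from Hypothesis #4, "at a nominal 0.05 level of significance with Bonferroni correction for four comparisons". BNP pilot data are from Table 2.

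**1. The plan's own figures.** Pooled SD of change, no ubiquinol against ubiquinol: √[(12 × 4986² + 7 × 1641²)/19] = 4086. Effect size: (-1494 - 4598)/4086 = -1.49, against -1.5 stated. For the combination the same method gives -1.31, against -1.3 stated. At 62 per group and alpha 0.0125, power exceeds 99.99% at 1.5 and is 91% at 0.7 (t-test). Both power statements reproduce.

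**2. The pilot effect on other scales.** The group without ubiquinol went from 1892 to 1892 + 4598 = 6490, a factor of 3.43. The ubiquinol group went from 2194 to 2194 - 1494 = 700, a factor of 0.32. In a lognormal simulation with these factors, about 41% of control readings at 12 weeks reach the cap. Power is still at least 99.9% for raw change (capped or not), log change and Mann-Whitney.

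**3. Skew.** Baseline SD/mean is 2381/1892 = 1.26 without ubiquinol and 1806/2194 = 0.82 with it. With log SD = √ln(1 + CV²), a lognormal fit gives log SDs of 0.97 and 0.72, medians of 1177 and 1694, and about 7% of baselines above 5000 in each. The N=4 combination group (116.5/2122 = 0.05) shows no skew.

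**4. A smaller proportional effect.** The documents give none, so these values are assumed: a 30% fall, no placebo drift, lognormal BNP as in step 3, within-patient log correlation ρ of 0.6 or 0.8, and readings set to the limit outside 5-5000. One run of 4,000 trials per row gives:

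| Log SD | ρ | Raw change, t-test | Raw change, Mann-Whitney | Log change, t-test | Log BNP adjusted for log baseline |
|---|---|---|---|---|---|
| 0.97 | 0.6 | 24% | 28% | 40% | 49% |
| 0.97 | 0.8 | 48% | 56% | 74% | 78% |
| 0.72 | 0.6 | 54% | 55% | 70% | 80% |
| 0.72 | 0.8 | 86% | 89% | 96% | 98% |

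Repeat runs differ by about one or two points. The ranges are about 24-85%, 28-88%, 39-96% and 49-98%.

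The log columns can be checked by hand without the cap. The effect is |ln 0.70| = 0.357. The SD is σ√[2(1 - ρ)] for log change and σ√(1 - ρ²) after adjustment. For σ = 0.974 and ρ = 0.6 the SDs are 0.871 and 0.779, the effect sizes 0.41 and 0.46, and the power 40% and 51%.

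**5. What causes the gap.** From raw to log change, power rises by 16, 26, 16 and 10 points down the table. Baseline adjustment adds up to about 10 more.

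**6. Lower BNP.** With an assumed median of 300, log SD 0.97 and the same 30% fall, raw change has 16-32% power and log change 40-76%. The gap does not depend on the very high pilot values.

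**7. The ceiling.** Across the rows of step 4, raw-change power is about 15-72% uncapped and 24-85% capped, because the cap trims the tail. On the log scale the cap costs one or two points at most. The ceiling does limit the estimate: from a baseline mean of 1892 with no capped baselines, the largest mean rise that can be recorded is 5000 - 1892 = 3108, below the 4598 behind the pilot effect size.

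**The case against.** The strongest reply is that the plan's power claim is arithmetically right and survives on any scale at its own effect size. That stands. A reader might infer that the 99% is a miscalculation; it is not. However, it rests on a nonrandomised comparison in which BNP without ubiquinol more than tripled in 12 weeks, and a randomised placebo arm on usual care need not do that.

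A reader might also infer that the 5000 pg/ml ceiling wastes power. The calculation shows the opposite for raw change.

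Nor is the fallback useless because negative changes have no logarithm. BNP can be logged at each visit and then subtracted, and that recovers most of the available power. If the fallback covers Hypothesis 5 and is used in this way, much of the loss disappears. What remains is that the plan does not say so.

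The evidence for skew is thin: means and SDs from groups of 13 and 8, an N=4 group without skew, and no statement of the pilot assay. Because BNP above 200 pg/ml is only one of several alternative entry criteria, trial values may be much lower than in the pilot, and the 7% above 5000 may not carry over. The gap between scales persists at lower BNP, but its size is uncertain. BNP also belongs to Aim 2, while Section C.3 gives priority to patient-centred outcomes.

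**Conclusion.** The point holds as a weakness of specification and efficiency for Hypothesis 5. At the pilot effect size nothing is lost. For an assumed 30% fall without placebo drift, the planned test has about 24-85% power, against 39-96% for log change and 49-98% for log BNP adjusted for log baseline. Not all of that gap is the cost of skew, since part of it comes from baseline adjustment. The ranges rest on lognormal BNP with pilot coefficients of variation and log correlations of 0.6-0.8, which the documents neither give nor exclude. The ceiling matters only because it truncates the effect in pg/ml and because out-of-range readings have no rule. The change should be made because it is cheap and uses a baseline that is already collected; the primary, patient-centred conclusions are not affected.

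**What to change.** In Section C.5, Hypothesis #5, name the analysis in advance: log BNP at 12 weeks, compared between groups with adjustment for log baseline BNP, for the same comparisons and Bonferroni level. Report geometric mean ratios with confidence intervals. Record readings below 5 or above 5000 pg/ml as such, treat them as censored at the limit, and report how many occur in each group and at each visit. Add a rank-based sensitivity analysis. State whether the fallback under Hypotheses #1 and #2 applies to Hypothesis 5. Alongside the 99% figure, give power for a range of proportional effects that do not rely on the chart review.

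This costs SAP wording only, with no extra patients, visits or samples. The downside is that the effect is reported as a ratio instead of a difference in pg/ml.

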All subjects will complete the demographic form at baseline. The KCCQ (Appendix 2) and Vigor scale from the Profile of Mood States (POMS) will be completed in CTSU visits at baseline and 12 weeks (Appendix 3) along with the subject's height and weight. The patient will be escorted to a private room and asked to remove clothing above the waist. A disposable gown will be provided and the patient will lay supine on the bed while an echocardiogram is completed. Approximately 0.5 ml of blood will be collected via finger stick to measure lactate, ATP, and BNP. Next, the subject will complete a 6MWT (Appendix 4, Borg scale). Approximately 2 hours will be required for each subject's visit to the CTSU. Follow-up calls will occur at 3, 6, and 9 weeks during the trial.

Potential Problem and Alternative Solutions. Serum CoQ10 and D-ribose values in some of the treatment patients might be below threshold levels at 6 weeks, possibly due to subject non-adherence. If this occurs, the Project Director, who is not blinded to the list of placebo and treatment subjects, will call and ask if there are any problems with consuming the ubiquinol and/or D-ribose. The Project Director and Research Associate will conduct a phone follow-up interview at 3, 6, and 9 weeks during the trial using a structured interview. Questions asked will relate to any side effects and compliance history in taking their capsules or powder.

Various cardiovascular risk factors will be recorded such as tobacco usage, diabetes mellitus, hypercholesterolemia, hypertension, and family history of cardiovascular disease. Smoking status will be recorded as either smoker or non-smoker. Patients who use tobacco will be given contact information for a tobacco/smoking cessation program. Diabetes mellitus will be determined by a history of the disease or use of medication for diabetes. Hypercholesterolemia will be defined as a fasting total serum cholesterol level ≥ 4.9 mmol/l or use of medication. Hypertension will be defined as either systolic or diastolic blood pressure $\geq 140/90$ mmHg or use of hypertensive medications.

C.3. Aims and Hypotheses.

AIM #1: *To determine the effects of oral ubiquinol, D-ribose, or a combination of the two administered during 12 weeks on symptoms accompanying low bioenergetics in patients with HFpEF.*

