echocardiography on patients with HFpEF have demonstrated more sensitive measurements of changes of LV structure than regular echocardiography. Speckle tracking consistently showed early diastolic strain rate, reduced peak strain, and fibrosis as evidenced by increased myocardial reflectivity, which parallels the degree of diastolic dysfunction.⁵⁰⁻⁵² In this study, a speckle tracking echocardiography technician will perform the echocardiograms during each visit (baseline and 12 weeks). Drs. [name] (an expert in speckle tracking research), [name], and [name] (cardiologists) will determine EF and the ratio of mitral peak velocity of early filling (E) to early diastolic mitral annular velocity (e') (E/e' ratio) (SV, EDV, EF) from the echocardiogram. Using speckle tracking software, we will measure myocardial deformation, rotation, torsion, strain, strain rate, and tissue velocity. Changes in the early apical diastolic untwisting rate (rotR) and negativity of time from apical peak diastolic untwist (trotR) to mitral valve opening (MVO) are two major variables that reflect diastolic function. Decreases in rotR and trotR are indications of diastolic dysfunction.⁵³ Speckle tracking analysis with two-dimensional imaging will be performed as previously described by Leitman et al. at high frame rate parasternal short-axis images at the level of the mitral valve to generate rotation and rotation rate data.⁴⁷ Frame-by-frame rotation and rotation rate will be exported in Excel, and the temporal data will be normalized to the percentage duration of systole and diastole separately as previously described by Nakai et al.⁵⁴ We anticipate that ubiquinol and/or D-ribose will change rotR, trotR, strain, strain rate, and tissue velocity.

Potential Problem and Alternative Solutions. One issue that might arise relates to scheduling the echocardiographic technician when the subject is available to come to the CTSU. A solution is to utilize an additional on-call echocardiographic technician should scheduling issues occur.

Hypothesis #4. Ubiquinol (600 mg daily), D-ribose (15 g daily), or a combination of the two will increase the distance that patients with HFpEF can walk in 6 minutes.

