Exercise-based testing is essential in evaluating the functional capacity and response to therapy and prognosis of patients with HF.⁵⁵ The 6-minute walking test (6MWT) is a simple clinical tool which has been shown to be linearly related to oxygen uptake.⁵⁶ The ease and cost of the 6MWT gives it advantages compared to other tests.⁵⁷ Mortality and morbidity in chronic HF have been predicted with the 6MWT. It was found that patients with a walking distance of less than 300 meters (325 yards) had 50% mortality at 1 year; the mortality of those walking more than 450 meters was less at 1 year. In addition, there was an inverse relationship between distance walked and hospitalization rates.⁵⁸

We will examine the effects of ubiquinol and/or D-ribose on the 6MWT at baseline and 12 weeks. Participants will be asked to wear appropriate clothes and shoes and walk the longest distance possible in 6 minutes. Prior to exercising, there will be a 10-minute rest period during which heart rate and blood pressure will be recorded. Subjects will walk indoors on a flat, straight 30-meter path marked every 3 meters, and they will be informed that they can slow down or stop at any time. A one-lap demonstration will be completed before the test begins. The distance walked will be recorded. Following the 6MWT, a 0.02 ml blood sample will be obtained for lactate measurement. Lactate provides a measure of the oxygen debt occurring during exercise and correlates directly with reported dyspnea and fatigue. The patient will also record perceived dyspnea and fatigue at baseline and at the end of each walk by using the Borg scale, where 0 = nothing at all, 5 = severe, and 10 = very severe. Words of encouragement will be offered during the walk and water provided afterward.

Hypothesis #5. Ubiquinol (600 mg daily), D-ribose (15 g daily), or a combination of the two will decrease venous blood B-type natriuretic peptide (BNP) levels in patients with HFpEF.

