Hypotheses #1 and #2. The change in the KCCQ Clinical Summary score from baseline to the end of the 12 weeks of treatment will be computed for each patient as KCCQ score at 12 weeks minus KCCQ score at baseline. A two-tailed independent samples t-test will test the null hypothesis of no difference in mean change between patients on ubiquinol and patients on placebo. Similar tests will be used to compare D-ribose with placebo, ubiquinol + D-ribose with placebo, and ubiquinol versus ubiquinol + D-ribose. Next, we state and justify the assumptions underlying our proposed sample size. Soto et al. (2004) conducted a study of 1516 patients and found that a 10-point decline in KCCQ scores had an important prognostic significance, in that patients whose KCCQ Clinical Summary scores declined by ≥ 10 points had a 107% increased risk of dying or being hospitalized during the next 12 weeks (event rate = 11.4% vs. 5.5%, $p < 0.001$).⁸⁵ Thus, we believe that an increase of at least 10 points with use of ubiquinol will be clinically important. In addition, our pilot study with ten subjects also found that, after 12 weeks of treatment, all subjects with ubiquinol or ubiquinol + D-ribose had an increase in the KCCQ Clinical Summary score of at least 10 points, which is consistent with the study findings of Soto et al. (2004). The combined estimated standard deviation for the increase was 12.3 points.

This implies that Cohen effect sizes of at least 0.81 ($= 10/12.3$) are clinically important. Therefore, a sample size of 62 subjects per group will provide at least 98% power to detect this or larger effect sizes at a nominal significance level of 0.05 (with Bonferroni correction for four comparisons).

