Hypothesis #3. The change in the E/e' ratio from baseline to the end of 12 weeks of treatment will be computed for each patient as E/e' ratio at 12 weeks minus E/e' ratio at baseline. A two-tailed independent samples t-test will be used to test the null hypothesis of no difference in mean E/e' ratio change between patients on ubiquinol and patients on placebo. Our pilot data (Table 2) showed a substantially strong and clinically important Cohen effect size of ubiquinol on E/e' ratio (-3.5). With 62 subjects per group, our t-test will have a very large power of 99% to detect this or larger effect sizes with a 0.05 level of significance (with Bonferroni correction for 4 comparisons, since both D-ribose alone and combined with ubiquinol will additionally be compared with placebo, and ubiquinol will be compared with ubiquinol + D-ribose). There are no studies comparing E/e' ratio on D-ribose versus placebo or on the combination of ubiquinol and D-ribose versus placebo. However, our sample sizes will be able to detect effect sizes of at least 0.7 in absolute value with at least 90% power. A study comparing D-ribose with dextrose found a significant improvement in atrial velocity with D-ribose, reporting means and SDs that suggest an effect size of about 0.85.⁹ Thus we are confident that our study will have sufficient power to investigate this other proxy of left ventricular diastolic function. Analogous computations and tests will be made to examine the effects of ubiquinol, D-ribose, and the combination of ubiquinol with D-ribose on PAP changes. The large and clearly clinically important effect size of ubiquinol on PAP observed in our pilot study (-2.8 ; Table 2) suggests that our sample sizes will provide 99% power for at least the ubiquinol-placebo comparison.

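### The main tests for Hypotheses #1 to #6 and the interaction regressions leave out the outcome's own baseline; adjusting for it would usually gain precision at almost no cost

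*Combined protocol and SAP*

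**What the plan says.** C.5 specifies the same kind of main test throughout.

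- **KCCQ Clinical Summary (Hypothesis #1):** "A two-tailed independent samples t-test will test the null hypothesis of no difference in mean change between patients on ubiquinol and patients on placebo". The same test compares D-ribose with placebo, the combination with placebo, and ubiquinol with the combination. Vigor (Hypothesis #2) is handled in the same way.
- **Diastolic function (Hypothesis #3):** "A two-tailed independent samples t-test will be used to test the null hypothesis of no difference in mean E/e' ratio change" between ubiquinol and placebo. Pulmonary artery pressure (PAP) is analysed analogously.
- **6MWT (Hypothesis #4):** a two-tailed t-test on mean change.
- **BNP (Hypothesis #5):** "two-tailed independent samples t-tests comparing changes in BNP from baseline to the end of 12 weeks".
- **Lactate/ATP (Hypothesis #6):** "The change in lactate/ATP ratio from baseline to 12 weeks will be computed for each patient", followed by a one-tailed t-test.

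Each outcome has four contrasts with Bonferroni correction, so the level is 0.05/4 = 0.0125. If assumptions fail, the section on Hypotheses #1 and #2 falls back on transformations or the Mann-Whitney test.

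Baselines are collected for all of these outcomes. The KCCQ and Vigor scale "will be completed in CTSU visits at baseline and 12 weeks" (C.2), and echocardiograms are done at both visits (C.3, Hypothesis #3). For walking distance: "We will examine the effects of ubiquinol and/or D-ribose on the 6MWT at baseline and 12 weeks". For BNP: "We will measure BNP concentration at each visit". C.5 states that lactate/ATP and E/e' are measured at both time points.

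The regressions under Statistical Analyses of Interaction model change on the two treatment indicators, their product, gender and race/ethnicity. Within that section, only the exploratory mediation model controls for baseline outcome values (E/e' and lactate/ATP).

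**The concern.** A t-test on change is an ANCOVA in which the slope of the week-12 value on baseline is fixed at 1. If the true slope differs from 1, part of the baseline variation stays in the change score as noise, and estimating the slope removes it. Every planned change score already needs the baseline value, so no new data are required.

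What is at stake is precision. It matters least for the KCCQ, the priority outcome. It matters more where the plan relies on its generic effect size of 0.7 (6MWT, lactate/ATP, and contrasts without pilot data). It also matters for the interaction test, for which the plan states no power and whose estimate has twice the variance of a pairwise contrast.

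**Working it through.** **Inputs.** From C.5: 62 completers per arm (69 less 10%), level 0.0125, KCCQ difference 10 with change SD 12.3, generic effect size 0.7. From Tables 1 and 2 in C.4: pilot baseline and change SDs. Assumed, because the documents do not give it: the baseline-to-week-12 correlation (rho) or slope.

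**1. The plan's own figures.** Noncentral t, 122 df, noncentrality d/√(2/62):
- d = 10/12.3 = 0.81 gives 97.6% (97.9% by the normal approximation; the plan says at least 98%).
- d = 0.7 gives 91.1% (the plan says at least 90%).

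Both reproduce to within rounding.

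**2. Two-arm ANCOVA, equal SDs at both visits.** Variance relative to the t-test = (1 + rho)/2 × [1 + 1/(2n − 4)], with n = 62 and 121 df. The finite-sample factor is 1 + 1/120 = 1.0083. Ordinary standard errors:

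| rho | variance ratio | power, d = 0.7, two-sided | power, d = 0.7, one-sided (Hypothesis #6) |
|---|---|---|---|
| t-test | 1 | 91.1% | 94.7% |
| 0.5 | 0.756 | 97.3% | 98.6% |
| 0.7 | 0.857 | 95.1% | 97.3% |
| 0.9 | 0.958 | 92.4% | 95.5% |
| 1 | 1.008 | 90.9% | 94.5% |

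**3. KCCQ.** With equal SDs, rho = 1 − SDchange²/(2 SDbase²). Table 1 gives 1 − 7.0²/(2 × 21.9²) = 0.95 and 1 − 13.2²/(2 × 28.3²) = 0.89, with five patients each. At those values power for 10 points goes from 97.6% to 97.8–98.1%.

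**4. E/e', PAP and BNP without the equal-SD assumption.** For a common slope b, the saving before the 0.8% finite-sample cost is (1 − b)² × (sum of the two arms' SDbase²)/(sum of their SDchange²). A contrast uses two arms, so the SDs are pooled over both. Example, E/e', ubiquinol against no ubiquinol: (6.1² + 2.4²)/(4.6² + 2.4²) = 42.97/26.92 = 1.60; times 0.25 gives 40% at b = 0.5.

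| Outcome, contrast | b = 0.5 | b = 0.7 | b = 0.9 |
|---|---|---|---|
| E/e', ubiquinol vs none | 40% | 14% | 1.6% |
| E/e', combination vs none | 41% | 15% | 1.7% |
| E/e', ubiquinol vs combination | 46% | 17% | 1.9% |
| PAP, ubiquinol vs none | 8.7% | 3.1% | 0.3% |
| PAP, combination vs none | 14.5% | 5.2% | 0.6% |
| BNP, ubiquinol vs none | 8.1% | 2.9% | 0.3% |
| BNP, combination vs none | 5.7% | 2.1% | 0.2% |

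The range in step 2 does not carry over to BNP: without ubiquinol, equal SDs would imply rho = 1 − 4986²/(2 × 2381²) = −1.19, which is impossible. At b = 0.9 the BNP and PAP savings are smaller than the 0.8% cost. D-ribose alone has no pilot data.

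**5. Interaction.** The estimate has variance 4σ²/n, against 2σ²/n for a pairwise contrast. Assume a 0.5 SD interaction, two-sided 0.05, and non-prognostic gender and race/ethnicity. Power is 50% unadjusted (244 df) and about 52%, 57% or 62% adjusted at rho 0.9, 0.7 or 0.5 (243 df).

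**6. Standard errors.** Null simulations at nominal 1.25%, 20,000 trials, with the larger change SD in the smaller arm:
- SDs 7.0 and 13.2, arms of 69 and 55: t-test and ordinary ANCOVA both reject about 1.9%; HC3 about 1.2%.
- SDs 1641 and 4986, arms of 69 and 55: both reject about 2.3–2.4%; HC3 about 1.2–1.4%.
- SDs 7.0 and 13.2, 62 per arm: 1.3% for both; HC3 1.2%.

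In power simulations at d = 0.7 (40,000 trials), HC3 cost about 0.5 points against ordinary errors when baseline did not predict change (90.8% to 90.3%). In the most extreme unequal-slope case (change-on-baseline slopes −0.8 and +0.8), power was 90.9% for the t-test, 90.7% for ordinary ANCOVA and 89.4% for HC3.

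**The case against.** The strongest reply is that this is a preference. The planned tests are valid, their power reproduces, and the priority outcome gains half a point at most. At the pilot effect sizes used for Vigor (1.8), E/e' (3.5), PAP (2.8) and BNP (1.5), power is already at its ceiling, and the interaction test remains weak after adjustment.

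All of those facts stand, and they limit the size of the point. They do not remove it. The large effect sizes come from small pilot samples, and those in Table 2 from nonrandomised comparisons; the plan itself falls back on 0.7 elsewhere. The KCCQ ceiling also depends on an SD from ten treated patients. If baseline SD were 25 and rho 0.8 (both assumed, equal SDs), the change SD would be 25 × √0.4 = 15.8, and power for 10 points would be 83.6% with the t-test and 87.5% with ANCOVA. Against this, the change costs almost nothing.

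Three stronger readings are tempting, and none is supported:
- **That the t-tests are wrong or the trial underpowered for its main contrasts.** Randomisation makes the comparison of mean change valid, and the power claims hold.
- **That every outcome gains as in step 2.** BNP and PAP against no ubiquinol do not, and single-arm SD ratios would misstate the range for E/e'.
- **That 1:1 allocation makes ordinary standard errors sufficient.** The plan expects attrition, and uneven loss with unequal SDs inflates the error rate of the t-test and of ordinary ANCOVA alike.

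**Conclusion.** The point holds as an improvement in precision. The main analyses of all six hypotheses, and the interaction regressions, leave out a covariate that is collected and usually informative.

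The size depends on a correlation that the documents do not give. At effect size 0.7, under equal SDs, it is about 1 to 6 points of power for rho from 0.9 to 0.5, less about half a point with HC3. For the KCCQ it is about half a point at most at the pilot's implied rho. On pilot SDs the E/e' variance saving is 40–46%, 14–17% or about 2% at slope 0.5, 0.7 or 0.9. For BNP and PAP against no ubiquinol it is about 6–14.5%, 2–5% or under 1%, which at slope 0.9 is no net gain. Interaction power improves but stays low. The pilot figures rest on 4 to 13 patients per group and are indicative only.

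**What to change.** Before unblinding, amend the SAP as follows.

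1. For each of Hypotheses #1 to #6, and for PAP, pre-specify for each of the four planned contrasts a two-arm ANCOVA of the week-12 value (or change) on treatment and that outcome's baseline. Keep the 0.0125 level and each test's planned sidedness.
2. Use HC3 standard errors.
3. Keep the existing fallback in a matching form: transform both the baseline and the week-12 value (for example log BNP), or use a rank-based analysis if assumptions fail.
4. Add the outcome's baseline to the interaction regressions.
5. Keep the planned t-tests as sensitivity analyses.

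Do not read the pairwise contrasts from one four-arm model with a common slope. In simulations with change-on-baseline slope 0 in the compared arms and −0.5 or −0.8 in the other two, its variance was 7% or 16% above that of the t-test.

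**Cost:** wording only, with no new data and no change in sample size. Each contrast loses one degree of freedom (122 to 121). If baseline does not predict change, power at 0.7 falls by about 0.2 points with ordinary errors (91.1% to 90.9%) or about 0.8 with HC3 (to about 90.3%). In the extreme unequal-slope case HC3 power is about 1.5 points below the t-test.
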